8.2.3 Other Laboratory Variables

Screening for pregnancy will be performed (urine β -HCG at the Screening and Treatment visits).

[REDACTED]

[REDACTED]

[REDACTED]

8.3 Serious Adverse Event and Unanticipated Adverse Device Effect Reporting

SAEs and UADEs must be reported within 24 hours of knowledge of the event to the Sponsor at the following email address:

[contact]

A full reporting of the event shall be provided within 2 working days of the event. The Sponsor is then responsible for notifying the IRB, as required.

8.4 Data Safety Monitoring Board

Not applicable.

8.4.1 Appropriateness of Measurements

The effectiveness and safety assessments planned for this study are widely used and generally recognized as reliable, accurate, and relevant.

9 STATISTICAL METHODS

The SAP will be developed and finalized before database lock and will describe the participant populations to be included in the analyses and procedures for accounting for missing, unused, and spurious data. This section is a summary of the planned statistical analyses.

Data will be summarized based on the nature of the data. Categorical (eg, gender, independent photographic review) data will be tabulated by category. The mean, standard error, maximum, and minimum will be tabulated for continuous data (eg, age). The significance level will be two-sided 0.05 for all statistical tests.

9.1 Determination of Sample Size

In this study, both arms and thighs will be evaluated by independent raters. The independent raters' evaluations will be combined into one clinical judgement on each arm and thigh. The evaluations on arms and thighs will be considered as independent.

[Rivers 2018](#) described that the rate of correct identification was 83%. Using 75% as the lower bound of the 95% CI, the $\frac{1}{2}$ -width of the 95% CI will be 8%.

Based on these assumptions, we will need 60 evaluable arms or 32 evaluable participants for the arm evaluations with the assumption that less than 10% of participants have only one arm evaluation available. The same number of participants for thigh evaluations will be needed.

With an assumption that only 80% of all subjects will have both arms and thighs treated, we will need 38 evaluable participants in total for the study. Adding a 10% attrition rate, we will need to enroll 42 participants in the study.

9.2 Populations for Analyses

1. PP population: The PP population will consist of all treated participants followed for 12 weeks and with weight change of no more than 5% of total body weight at the time the 12-week images are taken. Because a weight change of more than 5% will affect the images, the primary effectiveness analysis will be performed based on this study population. Participants who do not complete treatment on the upper arms and/or inner thighs will not be included in the effectiveness analyses.
2. AT population: The AT population will consist of all treated participants regardless of weight change, etc.
3. Safety population: The safety population will consist of all the treated participants with at least one safety evaluation after the treatment. This population should be identical to the AT population. All safety data analyses will be performed based on the safety population.

9.3 Statistical Analyses

9.3.1 Disposition, Baseline and Study Information

In general, disposition data, participant baseline and characteristics data, and concomitant therapy data will be summarized descriptively. The categorical variables will be presented with number and proportion while the continuous variables will be presented with mean, SD, median, minimum, and maximum.

9.3.1.1 Participant Disposition

The number of participants who have enrolled into the study, the number and percentage of participants who have had the procedure, the number and percentage of participants who have had all follow-up visits, and the number of participants who discontinued and the reasons for discontinuation will be summarized.

9.3.1.2 Participant Baseline and Characteristics

The demographics (age, sex, race [including determination of 1st or 2nd generation Chinese descent]) of participants will be summarized.

The summary on height, weight, and BMI will be also provided. The number and percentage of participants by BMI category (normal 18.5 to 25, overweight 25 to 30) will also be provided.

9.3.1.3 Concomitant Therapy

The concomitant therapy (drug and/or procedure) that a participant has during the study will be recorded and summarized.

9.3.1.4 Treatment Compliance

The treatment compliance will not be applicable in this study.

9.3.2 Effectiveness Analyses

The primary effectiveness analysis will be based on the PP population.

9.3.2.1 Primary Effectiveness Analysis

The number and proportion of participants with correct identification of baseline vs 12-week images of the upper arms by at least two out of three blinded, independent reviewers and the corresponding 95% CI of the proportion of participants with correct identification will be summarized.

9.3.2.2 Secondary Analyses

The number and proportion of participants with correct identification of baseline vs 12-week images of the inner thighs by at least two out of three blinded, independent reviewers and the

corresponding 95% CI of the proportion of participants with correct identification will be summarized.

Participants who have reported ‘Very satisfied’ or ‘Satisfied’ on each of the CoolSculpting participant questionnaires (upper arms and inner thighs) for question #1 (overall satisfaction) will be categorized as ‘Satisfied.’ The numbers and proportions will be summarized and the 95% CI of the proportions will be provided.

Fat reduction at 12 weeks compared to baseline will be summarized descriptively.

9.3.3 Safety Analyses

The numbers and proportions of participants with AEs, SAEs, ADEs, and SADEs will be summarized. The numbers and proportions of participant-reported pain scores (0 to 10 scale) will be summarized.

9.3.3.1 Subgroup Analyses

Subgroup analyses will be documented in the SAP.

9.3.4 Interim Analyses

No interim analyses are planned for this study.

9.4 Protocol Deviations

Major protocol deviations will be determined before database lock. Details will be outlined in the SAP.

10 QUALITY ASSURANCE AND QUALITY CONTROL

10.1 Audit and Inspection

Study centers and study documentation may be subject to Quality Assurance audit during the course of the study by the sponsor or its nominated representative. In addition, inspections may be conducted by regulatory authorities at their discretion

10.2 Monitoring

Data for each participant will be recorded on a CRF. Data collection must be completed for each participant who signs an ICF and is administered study treatment.

In accordance with current GCP, the study monitor will carry out source document verification at regular intervals to ensure that the data collected in the CRF are accurate and reliable.

The investigator must permit the monitor, the independent ethics committee (IEC)/IRB, the sponsor's internal auditors, and representatives from regulatory authority's direct access to all study-related documents and pertinent hospital or medical records for confirmation of data contained within the CRFs

10.3 Data Management and Coding

The sponsor or sponsor's agent will be responsible for activities associated with the data management of this study. This will include setting up a relevant database and data transfer mechanisms, along with appropriate validation of data and resolution of queries. Data generated within this clinical study will be handled according to the relevant standard operating procedures of the data management and biostatistics departments of sponsor or agent.

Study centers will enter data directly into an EDC system by completing the CRF via a secure internet connection. Data entered into the eCRF must be verifiable against source documents at the study center. Data to be recorded directly on the eCRF will be identified and the eCRF will be considered the source document. Any changes to the data entered into the EDC system will be recorded in the audit trail and will be FDA CFR 21 Part 11 compliant.

Missing or inconsistent data will be queried in writing to the investigator for clarification. Subsequent modifications to the database will be documented.

11 RECORDS AND SUPPLIES

11.1 Device Accountability

Not applicable.

11.2 Financing and Insurance

Financing and insurance of this study will be outlined in a separate agreement between the sponsor and investigator's site.

12 ETHICS

12.1 Independent Ethics Committee or Institutional Review Board

Before initiation of the study at each study center, the protocol, the ICF, other written material given to the participants, and any other relevant study documentation will be submitted to the appropriate IEC/IRB. Written approval of the study and all relevant study information must be obtained before the study center can be initiated. Any necessary extensions or renewals of IEC/IRB approval must be obtained for changes to the study such as amendments to the protocol, the ICF, or other study documentation. The written approval of the IEC/IRB together with the approved ICF must be filed in the study files.

The investigator will report promptly to the IEC/IRB any new information that may adversely affect the safety of the participants or the conduct of the study. The investigator will submit written summaries of the study status to the IEC/IRB as required. On completion of the study, the IEC/IRB will be notified that the study has ended.

12.2 Ethical Conduct of the Study

The investigator(s) and all parties involved in this study should conduct the study in adherence to the ethical principles based on the Declaration of Helsinki, GCP, and the applicable national and local laws and regulatory requirements.

12.3 Informed Consent

The process of obtaining informed consent must be in accordance with applicable regulatory requirement(s) and must adhere to GCP.

The investigator is responsible for ensuring that no participant undergoes any study-related examination or activity before that participant has given written informed consent to participate in the study.

The investigator or designated personnel will inform the participant of the objectives, methods, anticipated benefits, and potential risks and inconveniences of the study. The participant should be given every opportunity to ask for clarification of any points s/he does not understand and, if necessary, ask for more information. At the end of the interview, the participant will be given ample time to consider the study. Participants will be required to sign and date the ICF. After signatures are obtained, the ICF will be kept and archived by the investigator in the investigator's study file. A signed and dated copy of the participant ICF will be provided to the participant or their authorized representative.

It should be emphasized that the participant may refuse to enter the study or to withdraw from the study at any time, without consequences for their further care or penalty or loss of benefits to which the participant is otherwise entitled. Participants who refuse to give or who withdraw written informed consent should not be included or continue in the study.

If new information becomes available that may be relevant to the participant's willingness to continue participation in the study, a new ICF will be approved by the IEC(s)/IRB(s). The study

participants will be informed about this new information and reconsent will be obtained.

12.4 Participant Confidentiality

Monitors, auditors, and other authorized agents of the sponsor and/or its designee, the IEC(s)/IRB(s) approving this research, as well as that of any other applicable agency(ies), will be granted direct access to the study participants' original medical records for verification of clinical study procedures and/or data, without violating the confidentiality of the participants to the extent permitted by the law and regulations. In any presentations of the results of this study or in publications, the participant's identity will remain confidential.

13 REPORTING AND PUBLICATION, INCLUDING ARCHIVING

Essential documents are those documents that individually and collectively permit evaluation of the study and quality of the data produced. After completion of the study (end of study defined as the date of the last visit of the last participant), all documents and data relating to the study will be kept in an orderly manner by the investigator in a secure study file. This file will be available for inspection by the sponsor or its representatives. Essential documents should be retained for 2 years after the final marketing approval or for at least 2 years since the discontinuation of clinical development of the investigational product. It is the responsibility of the sponsor to inform the study center when these documents no longer need to be retained. The investigator must contact the sponsor before destroying any study-related documentation. In addition, all participant medical records and other source documentation will be kept for the maximum time permitted by the hospital, institution, or medical practice.

The sponsor must review and approve any results of the study or abstracts for professional meetings prepared by the investigator(s). Published data must not compromise the objectives of the study. Data from individual study centers in multi-center studies must not be published separately.

15.2 CoolSculpting Procedure Training Guides

The purpose of this statistical analysis plan (SAP) is to ensure that the data listings, summary tables and figures which will be produced, and the statistical methodologies that will be used, are complete and appropriate to allow valid conclusions regarding the study objectives. All analyses included within this plan will be descriptive in nature; there are no plans for statistical hypothesis testing or comparisons between groups.

2.1. Responsibilities

██████████ will perform the statistical analyses and are responsible for the production and quality control of all tables, figures and listings.

2.2. Timings of Analyses

The primary analysis of safety and effectiveness is planned after all participants complete the final study visit or terminate early from the study. Unless otherwise specified, the analysis includes all data collected in the database through the time of the database lock.

This document is confidential.

3. Study Objectives

The objective of this study is to evaluate the safety and effectiveness of the Allergan CoolSculpting system using CoolAdvantage and CoolAdvantage Petite applicators for non-invasive fat reduction (NIFR) of the upper arms and inner thighs in participants of Chinese descent.

3.1. Brief Description

This is a multi-center, prospective, open-label, nonrandomized, interventional cohort, medical device post-marketing study.

The purpose of this study is to collect meaningful clinical data for the use of CoolSculpting in participants of Chinese descent (to be conducted in Canada) using the current CoolAdvantage and CoolAdvantage Petite applicators for the upper arm and inner thigh body areas.

Participants will undergo a CoolSculpting treatment in an outpatient clinical setting. A treatment is comprised of timed segments of cooling. Treatments will be administered according to the User Manual CoolSculpting System that has been prepared for specific countries. The CoolSculpting System, also labelled as the ZELTIQ System or the ZELTIQ Breeze System, is a non-invasive cooling device that applies controlled cooling to a treatment site on the participant's skin.

Approximately 42 participants will be enrolled at approximately 2-3 sites.

Screening (8 days), enrollment, and follow-up is expected to take approximately 3 months in total for each participant.

Participants who do not comply with the protocol or who withdraw consent will not be replaced.
Participants who stop study treatment for any other reason will not be replaced.

3.2. Participant Selection

To be eligible to participate, participants must meet all of the inclusion criteria and none of the exclusion criteria listed below.

3.2.1. Inclusion Criteria

The inclusion criteria are detailed in section 6.3.2 of the protocol.

3.2.2. Exclusion Criteria

The exclusion criteria are detailed in section 6.3.3 of the protocol.

3.3. Determination of Sample Size

In this study, both arms and thighs will be evaluated by independent raters. The independent raters' evaluations will be combined into one clinical judgement on each arm and thigh. The evaluations on arms and thighs will be considered as independent.

A previous study described that the rate of correct identification was 83%. Using 75% as the lower bound of the two-sided exact 95% confidence interval (CI), the $\frac{1}{2}$ -width of the two-sided exact 95% CI will be 8%.

This document is confidential.

Based on these assumptions, we will need 60 evaluable arms or 32 evaluable participants for the arm evaluations with the assumption that less than 10% of participants have only one arm evaluation available. The same number of participants for thigh evaluations will be needed.

With an assumption that only 80% of all participants will have both arms and thighs treated, we will need 38 evaluable participants in total for the study. Adding a 10% attrition rate, we will need to enroll 42 participants in the study.

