2. As-treated (AT) population: The AT population will consist of all treated participants regardless of weight change, etc.

3. Safety population: The safety population will consist of all the treated participants with at least one safety evaluation after the treatment. This population should be identical to the AT population. All safety data analyses will be performed based on the safety population.

Sample Size Determination

In this study, both arms and thighs will be evaluated by independent raters. The independent raters' evaluations will be combined into one clinical judgement on each arm and thigh. The evaluations on arms and thighs will be considered as independent.

A previous study described that the rate of correct identification was 83%. Using 75% as the lower bound of the 95% confidence interval (CI), the $\frac{1}{2}$ -width of the 95% CI will be 8%.

Based on these assumptions, we will need 60 evaluable arms or 32 evaluable participants for the arm evaluations with the assumption that less than 10% of participants have only one arm evaluation available. The same number of participants for thigh evaluations will be needed.

With an assumption that only 80% of all subjects will have both arms and thighs treated, we will need 38 evaluable participants in total for the study. Adding a 10% attrition rate, we will need to enroll 42 participants in the study.

Statistical Analyses

In general, disposition data, participant baseline and characteristics data, and concomitant therapy data will be summarized descriptively. The categorical variables will be presented with number and proportion while the continuous variables will be presented with mean, standard deviation, median, minimum, and maximum.

The primary effectiveness analysis will be based on the PP population. The number and proportion of participants with correct identification of baseline vs 12-week images of the upper arms by at least two out of three blinded, independent reviewers and the corresponding 95% CI of the proportion of participants with correct identification will be summarized.

The number and proportion of participants with correct identification of baseline vs 12-week images of the inner thighs by at least two out of three blinded, independent reviewers and the corresponding 95% CI of the proportion of participants with correct identification will be summarized.

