4.1. Primary Endpoint

Correct identification of baseline versus 12-week treatment images of the upper arms by at least two out of three blinded, independent reviewers. Success will be defined as at least 75% correct identification of the pre-treatment images.

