8.1. Primary Effectiveness Analysis

The number and proportion of arms with correct identification of baseline vs. 12-week images of the upper arms by at least two out of three blinded, independent reviewers. Success will be defined as at least 75% correct identification of the pre-treatment images. The corresponding two-sided exact 95% CI of the proportion of arms with correct identification will be summarized.

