1. 'Day 1' is used in this SAP for the study day where 'Day 0' is used in the protocol.
2. As per section 9.2 of the protocol, safety population was defined as 'The safety population will consist of all the treated participants with at least one safety evaluation after the treatment'; AT was defined as 'The AT population will consist of all treated participants regardless of weight change, etc.'. These two populations will consist same participants . Therefore, in the SAP, only one of them is defined as 'The safety population will consist of all the treated participants'.
3. Sample size is calculated based on number of arms. 'participants' is a typo in the protocol. So, the term 'participants' is replaced by 'arms' appropriately. Similarly, 'participants' is a typo in the protocol for primary and secondary effectiveness analyses. The term 'participants' is replaced by 'arms' or 'thighs', respectively. These are administrative changes.

This document is confidential.

[figure not shown]
13. Reference List

To be updated.

[figure not shown]
This document is confidential.

[figure not shown]
This document is confidential.

This document is confidential.

[figure not shown]
This document is confidential.

17. Index of Figures

No Figures

This document is confidential.

[figure not shown]

This document is confidential.

[figure not shown]
19. Table, Listing, and Figure Shells

This table, figure and listing shells will be provided as a separate document.

[figure not shown]
This document is confidential.

[figure not shown]
This document is confidential.

[figure not shown]
This document is confidential.

This document is confidential.

This document is confidential.

This document is confidential.

This document is confidential.

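### At an 83% rate, 60 arms do not give a 95% CI with half-width 8% and lower bound 75%; the exact CI named in the SAP runs from about 71% to 92%.

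*SAP*

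**What the plan says.** SAP 3.3 (Determination of Sample Size) takes 83% as the expected rate of correct identification, from a previous study. It then sets the precision target: "Using 75% as the lower bound of the two-sided exact 95% confidence interval (CI", with a half-width of 8% for the same two-sided exact interval. From these it concludes that "we will need 60 evaluable arms or 32 evaluable participants for the arm evaluations".

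Protocol 9.1 uses the same 83%, 75%, 8% and 60, but writes "Using 75% as the lower bound of the 95% CI" with no method or sidedness. The synopsis does likewise: "Using 75% as the lower bound of the 95% confidence interval (CI".

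Four other statements in the SAP bear on this:

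- Section 8.1 fixes the interval to be reported: "The corresponding two-sided exact 95% CI of the proportion of arms with correct identification will be summarized".
- Section 12 settles the unit: "Sample size is calculated based on number of arms".
- Section 2 says "All analyses included within this plan will be descriptive in nature", and that no hypothesis testing is planned.
- Section 4.1 gives the success rule: "Success will be defined as at least 75% correct identification of the pre-treatment images". No condition on a confidence limit is attached.

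**The concern.** Section 3.3 states every input, so the figure of 60 can be checked directly, and it looks too small for a two-sided 95% interval of that width. An exact interval is also asymmetric at 83%: its lower arm is longer than its upper arm. A half-width of 8 points and a lower limit of 75% are therefore two different conditions, which section 3.3 treats as one.

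Because the analysis is descriptive, this precision statement is the only quantitative basis given for the size of the trial. If 60 arms do not deliver it, the report will show a wider interval than the plan promised, even if the planning rate is observed exactly. The figure 75% also serves twice, as the sizing lower bound and as the success threshold, and the documents do not say how the two relate. A reader could take success to mean that the lower confidence limit cleared 75%.

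**Working it through.** **Inputs.** p = 0.83, d = 0.08, lower limit 0.75, two-sided exact 95% CI, n = 60 arms (all SAP 3.3); unit = arms (SAP 12). Arms are first treated as independent.

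**1. Reproducing the plan's 60.** The normal-approximation formula is n = z² p(1−p)/d², with p(1−p) = 0.83 × 0.17 = 0.1411 and d² = 0.0064.

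- z = 1.96 (two-sided 95%): 3.8416 × 0.1411 / 0.0064 = 84.7, so 85 arms.
- z = 1.645 (two-sided 90% or one-sided 95%): 2.706 × 0.1411 / 0.0064 = 59.7, so 60 arms.

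The stated 60 matches only the second line. The documents do not say that z = 1.645 was used.

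**2. What 60 arms give at two-sided 95%.**

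| Method | Rate | 95% CI | Half-width (points) |
|---|---|---|---|
| Normal | 83% | 73.5% to 92.5% | 9.5 |
| Wilson | 83% | 71.6% to 90.4% | 9.4 |
| Agresti-Coull | 83% | 71.4% to 90.6% | 9.6 |
| Jeffreys | 83% | 72.1% to 90.9% | 9.4 |
| Exact (Clopper-Pearson) | 83%, interpolated | 71.1% to 91.5% | 10.2 |
| Exact (Clopper-Pearson) | 50/60 = 83.3% | 71.5% to 91.7% | 10.1 |

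None reaches 75% or 8 points. At 50/60 the exact lower limit equals 75% only at a two-sided confidence level of about 83%.

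**3. Arms needed for the stated exact interval at 83%.**

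- Half-width at most 8 points: about 96 arms. The lower limit is then 74.0%.
- Lower limit at least 75%: about 119 arms, interpolating the count. With whole-number counts the condition is first met at 114 and holds at every n from 128.

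**4. How often 60 arms would reach a lower limit of 75%.** The exact lower limit is 73.4% at 51/60 and 75.4% at 52/60, so at least 52 correct are needed. At a true rate of 83%, P(X ≥ 52) = 0.288.

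**5. The most arms the enrolment could supply.** All 42 participants, both arms, no attrition, is 84 arms. The exact CI at 70/84 is 73.6% to 90.6%, half-width 8.5 points. This still misses both targets.

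**6. Correlation between a participant's two arms.** The documents give no value, so a range of 0 to 0.6 is assumed here. With 30 pairs the normal half-width is 1.96 × √(0.1411 × (1 + ρ)/60). This is 9.5 points at ρ = 0 and 12.0 points at ρ = 0.6.

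**The case against.** The strongest reply is that nothing downstream changes. Success is written without a confidence limit, no tests are planned, and SAP 8.1 already commits to the correct exact interval, so readers will see the true precision whatever section 3.3 says. That is right, and it limits the consequence to the stated rationale. It does not make the rationale correct.

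A second reply is that the protocol names neither sidedness nor method, and that a one-sided 95% normal limit of 75% does give 60 arms. The protocol is indeed the weaker case. But the same sentence speaks of a half-width, and Protocol section 9 sets a two-sided 0.05 level (for tests). The SAP says two-sided exact twice. Even an exact one-sided 95% limit at 50/60 is 73.4%.

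A third is that 60 is a minimum and more arms are expected. Suppose 38 participants are evaluable, 80% have both areas treated, and the rest split evenly between arms and thighs (an assumption). Then 30.4 + 3.8 = 34.2 have arms treated, and 10% with a single arm gives 34.2 × 1.9 ≈ 65 arms. The exact CI at 54/65 is 71.7% to 91.2%, half-width 9.8 points. The target is still missed.

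Finally, the correlation range is assumed, and the possible misreading of success is a matter of clarity, not arithmetic. Both points stand. The arithmetic conclusion needs neither.

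**Conclusion.** The concern holds. At the planning rate, 60 arms give an exact 95% half-width of about 10 points instead of 8, and a lower limit of about 71.5%, some 3.5 points below the stated 75%. The shortfall is 25 arms by the normal formula (85 − 60), about 36 for the exact half-width (96 − 60) and about 59 for the exact lower limit (119 − 60).

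These figures assume independent arms, which favours the plan; positive correlation within participants would widen the interval. The origin of the 60 in z = 1.645 is inferred. The success rule, the planned analysis and the CI to be reported are unchanged.

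**What to change.** Keep the enrolment and correct the statement in SAP 3.3, Protocol 9.1 and the synopsis. Suggested text: *With about 60 evaluable arms and an observed rate of about 83%, the two-sided exact 95% CI is about 71% to 92% (half-width about 10 points), before allowing for within-participant correlation.* In the same edit, remove the lower bound of 75% and the half-width of 8%, and present 60 arms as the planned number, not as derived from them.

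Add one sentence making clear that the 75% in the success definition (SAP 4.1 and 8.1) is separate from the sizing limit, and stating what it applies to. If it applies to the observed proportion, the probability of meeting it (at least 45 of 60) could usefully be given: about 96%, 57% and 24% at true rates of 83%, 75% and 70% with independent arms. With an assumed correlation of 0.6 these become about 92%, 56% and 30%, so the caveat should go with them.

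The cost is one reworded paragraph in three places and one clarifying sentence. No participants are added and no analysis changes. The stated precision becomes less favourable.
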